### **8.5.2. Safety Monitoring Rules for Platelet Count Results**

Platelet count will be monitored at least every week during the Treatment Period and at the following visits in the Post-Treatment Period, Study Day 57/Study Week 9, Study Day 64/ Study Week 10, Study Day 78/Study Week 12, Study Day 92/Study Week 14, Study Day 120/Study Week 18, and Study Day 141/Study Week 21. The Investigator should review all platelet count results within 48 hours of receipt. In case of platelet reduction to below  $75,000/\text{mm}^3$ , the platelet monitoring rule defined in Stopping rules (Section 8.6.3) should be followed and additional laboratory investigations may be conducted [Table 5](#).

Please refer also to [Table 6](#).

Any uninterpretable platelet count result must be rechecked and determined not to have met a stopping rule before dosing can continue.

**Table 5: Additional Labs to be Performed in the Event of a Platelet Count < 75,000/mm^3**

To Be Performed at Local Lab
Peripheral smear (should be performed locally, fixed and sent to central lab for review)
Fibrinogen split products or D-dimer on fresh blood
To be performed at Central Lab
Citrated sample for platelets
Coagulation panel (PT/INR, aPTT)
CBC with reticulocytes and mean platelet volume (MPV)
Serum B12 and folate
Fibrinogen
von Willebrand factor
Total globulins, total IgA, IgG and IgM
Complement: total C3, total C4, Bb, C5a
To Be Performed at Local Lab
hsCRP
Serology for:
HBV, HCV, HIV (if not done for screening)
Rubella
CMV
EBV
Parvo B19
Helicobacter pylori (IgG serum test)
Auto-antibody screen:
Antiphospholipid
Rheumatoid factor
Anti-dsDNA
Anti-thyroid
To Be Performed at Specialty Lab(s)
Antiplatelet antibodies and Anti-PF4 assay
Anti-ASO antibody

Note: The above labs may change as additional data is assessed, and sites will be updated regarding any changes.

### 8.5.3. Safety Monitoring for Minor Bleeding Events

Minor bleeding events are those that do not fulfill the criteria for major bleeding (MB) or clinically relevant, non-major bleeding events (which are defined in Section 8.6.3), for example

excess bruising, petechiae, gingival bleeding on brushing teeth. If a minor bleeding event occurs, additional testing of coagulation parameters (aPTT, PT, INR) and platelet count should be performed.

#### **8.5.4. Safety Monitoring for Potassium**

In the event of a potassium measurement  $\geq 5.5$  mmol/L at any time during the study (Treatment or Post-Treatment Period), the initial measurement(s) should be confirmed. If the initial potassium measurement is confirmed to be  $\geq 5.5$  mmol/L study drug is to be held. An ECG evaluation should be performed if the value is confirmed and signs of hyperkalemia should be assessed (delayed conduction, heart block, arrhythmias). If new signs consistent with hyperkalemia are present, proceed to stopping rules. The subject will start oral hydration with 1-liter fluids not containing potassium to induce diuresis. Measure potassium frequently until documented to be  $< 5.5$  mmol/L. Dosing with study drug may continue after a confirmed potassium measurement  $< 5.5$  mmol/L with Investigator and Sponsor Medical Monitor or designee consultation.

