### 8.5. Safety Monitoring Rules

Please refer also to the ‘Guidance for Investigator’ section of the Investigator’s Brochure.

For the purposes of the renal and platelet safety monitoring rules, Baseline is defined as:

- The last non-missing measurement prior to the first dose

In addition to the standard monitoring of clinical safety parameters, the following guidelines are provided for the monitoring of selected parameters chosen based on preclinical and clinical observations.

Confirmation Guidance: At any time during the study (Treatment or Post-Treatment Periods), the initial clinical laboratory results meeting the safety monitoring criteria presented below **must be confirmed** by performing measurements (ideally in the same laboratory that performed the initial measurement) on new specimens. All new specimen collections should take place as soon as possible (ideally within 3 days of the initial collection). For stopping rules, if the initial laboratory result is observed during the Treatment Period, the results from the retest **must be available** prior to administering the next dose of Study Drug (ISIS 757456 or placebo).

Re-dosing Guidance: Subjects with initial laboratory test values that reach a stopping rule must not be re-dosed until the re-test results are available. In general, subjects who do not meet the stopping rules based upon retest may continue dosing. However, the Investigator and the Sponsor Medical Monitor (or appropriately qualified designee) should confer as to whether additional close monitoring of the subject is appropriate. If any of the stopping criteria described below (refer to Section 8.6.1 to Section 8.6.5) are met, the subject will be permanently discontinued from further treatment with Study Drug (ISIS 757456 or placebo), evaluated fully as outlined below and in consultation with the Sponsor Medical Monitor or appropriately qualified designee, and will be followed up in accordance with Section 8.8 of the protocol.

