#### 8.6.4. Stopping Rule for Potassium

In the event of confirmed potassium of  $\geq 6.0$  mmol/L or  $\geq 5.5$  mmol/L *with* new ECG changes consistent with hyperkalemia at any time during the study, dosing of a subject with Study Drug will be stopped permanently. The subject should stop any medications (e.g., ACE/ARB) or high K+ diet/supplements affecting potassium levels. Measure potassium frequently until documented to be  $< 5.5$  mmol/L. If there are ECG changes consistent with hyperkalemia or muscle weakness the subject should be admitted to the hospital. The Investigator may consider obtaining a nephrology consultation with consideration for dialysis to treat hyperkalemia. Additional consultation of the Investigator with the Sponsor Medical Monitor may be considered to individualize treatment plan.

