**APPENDIX A. SCHEDULE OF PROCEDURES**

**Appendix A Schedule of Procedures**

	Screen	Treatment Period (8 Weeks)									Post-Treatment Period (13 Weeks)					
Study Week		Wk1	Wk2	Wk3	Wk4	Wk5	Wk6	Wk7	Wk8	Wk9	Wk10	Wk12	Wk14	Wk18	Wk21	
Study Day	D-28 to D-1	D1	D3	D8	D15	D22	D29	D36	D43	D50	Treatment Early Term  / D57	D64	D78	D92	D120	PT Early Term  / D141
Visit Window (Days)	NA	NA	+2	± 2	± 2	± 2	± 2	± 2	± 2	± 2	± 2	± 2	± 2	± 5	± 5	± 5
Scheduled Visit #	1	2	3	4	5	6	7	8	9	10	11	12	13	14	15	16
Informed Consent	X															
Inclusion/Exclusion	X	X a														
Medical History	X															
Low Sodium Diet Education	X	← Continuous Counseling & Monitoring →														
CVD Risk Factors	X															
Body Weight and Height 	X	X									X					X
Physical Exam 	X	X									X					X
ECG (12-Lead)	X										X					
Vital Signs (clinic) 	X	X a	X a	X a	X a	X a	X a	X a	X a	X a	X	X	X	X	X	X
HIV, Hep B & C	X															
FSH 	X															
Pregnancy Test 	X															
Chemistry Panel (Fasting) 	X	X a		X a	X a	X a	X a	X a	X a	X a	X	X	X	X	X	X
Renal Urine Biomarkers and Archived Urine Sample 	X	X a		X a	X a	X a	X a	X a	X a	X a	X	X	X	X	X	X
TSH, FT3, FT4	X															
Hematology 	X	X a		X a	X a	X a	X a	X a	X a	X a	X	X	X	X	X	X
Urinalysis 	X	X a		X a	X a	X a	X a	X a	X a	X a	X	X	X	X	X	X
Plasma AGT	X	X a	X a	X a	X a	X a	X a	X a	X a	X a	X	X	X	X	X	X
Exploratory	X	X a				X a					X		X	X	X	X
hsCRP		X a									X					X
PT, INR, aPTT	X															
Study Drug Administration		X	X	X	X	X	X	X	X	X						

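### An initial potassium of 5.5 to below 6.0 mmol/L triggers a retest, but nothing requires the result before the next dose

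*Combined protocol and SAP*

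**What the plan says.** Protocol 8.5.4 sets a monitoring threshold of 5.5 mmol/L. A value at or above it is to be repeated. The hold depends on the repeat: "If the initial potassium measurement is confirmed to be" at or above 5.5, drug is withheld. The ECG is also ordered only after confirmation. The section closes with the condition for going on: "Dosing with study drug may continue after a confirmed potassium measurement" below 5.5, after the Investigator and the Medical Monitor have conferred.

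Protocol 8.5 gives the general rules. Repeating a value that meets a monitoring criterion is mandatory: "All new specimen collections should take place as soon as possible (ideally within 3 days of the initial collection"). Two sentences link the repeat to dosing, and both are restricted in scope:

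- Confirmation guidance: "For stopping rules, if the initial laboratory result is observed during the Treatment Period, the results from the retest" have to be in hand before the next dose.
- Re-dosing guidance: "Subjects with initial laboratory test values that reach a stopping rule must not be re-dosed until the re-test results are available".

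Protocol 8.6.4 is the potassium stopping rule. It applies to a confirmed value of 6.0 mmol/L or above, or to 5.5 or above with "new ECG changes consistent with hyperkalemia at any time during the study, dosing of a subject with Study Drug will be stopped permanently".

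**The concern.** An initial value between 5.5 and 6.0 mmol/L falls between these rules. It is high enough that the plan would withhold drug if it were confirmed. It is too low to count as reaching a stopping rule unless new ECG changes are already known, so neither pre-dose requirement in 8.5 applies to it.

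Every subject takes an ACE inhibitor or an ARB (5.1, criterion 8), and the trial adds a further agent acting on the same system. Section 2.2 names hyperkalemia as a complication of combining RAAS agents. It also expects this drug to spare the kidney, which would lower the risk, but that is still an expectation. A subcutaneous dose cannot be taken back once given. If the retest then confirms 5.5 or above, the subject has received a dose that the plan's own rule would have withheld.

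**Working it through.** The plan states no figure to reproduce. The check has two parts: which rule applies at each potassium level, and how much time lies between a potassium draw and the next dose.

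**Which rule applies to an initial value, before any retest**

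| Initial potassium (mmol/L) | Retest required? | Retest result required before next dose? |
|---|---|---|
| Below 5.5 | No | No |
| 5.5 to below 6.0, no known new ECG change | Yes (8.5, 8.5.4) | No |
| 5.5 to below 6.0, new ECG change already known | Yes | Yes (8.6.4 reached, so 8.5 applies) |
| 6.0 or above | Yes | Yes (8.6.4 reached, so 8.5 applies) |

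The third row will seldom arise. Section 8.5.4 orders the ECG only after confirmation, and Appendix A schedules ECGs only at Screening and Day 57. The redraw rules in 6.2 and Appendix A footnote 7 cover uninterpretable platelet, creatinine and liver enzyme results, and 8.5.2 covers platelets. None covers a high potassium.

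**Results followed by another dose**

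The Appendix A row "Chemistry Panel (Fasting") has a pre-dose sample at 8 of the 9 dosing visits: Days 1, 8, 15, 22, 29, 36, 43 and 50. Day 50 is the last dose, so 8 − 1 = 7 results precede a later dose. Six are on drug (Days 8 to 43) and one is pre-drug (Day 1).

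**Time from draw to next dose**

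The row "Visit Window (Days") gives ±2 for the weekly dosing visits and +2 for Day 3. I assume that windows count from the nominal day. With offsets a (this visit) and b (next visit), each from −2 to +2:

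weekly interval = 7 + b − a

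| Interval (days) | 3 | 4 | 5 | 6 | 7 | 8 | 9 | 10 | 11 |
|---|---|---|---|---|---|---|---|---|---|
| Offset pairs (of 25) | 1 | 2 | 3 | 4 | 5 | 4 | 3 | 2 | 1 |

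Three of the 25 pairs give 4 days or fewer, and 22 give 5 or more. These are counts of combinations, not probabilities.

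With the retest collected at the 3-day ideal limit:

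- Weekly, nominal: 7 − 3 = 4 days left.
- Weekly, shortest: 3 − 3 = 0 days left.
- Day 1 to the Day 3 loading dose, an interval of 2 to 4 days: 2 − 3 = −1 to 4 − 3 = +1 day left.

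These margins run to specimen collection. Laboratory turnaround, which the documents do not give, shortens them.

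The Day 1 to Day 3 interval is the tightest, but its sample is taken before any drug. Screening excludes potassium above 4.9 (5.2, criterion 14e), so a Day 1 value of 5.5 needs a rise of at least 5.5 − 4.9 = 0.6 mmol/L without Study Drug.

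**The case against.** The strongest reply is that the closing sentence of 8.5.4 already bars dosing. It speaks of continuing rather than restarting, and the section opens with an initial value, so a cautious site could read it as: retest, and go on only if below 5.5. That reading is possible, but it does not fit the order of the section. The sentence comes after the hold, the ECG, hydration and repeat measurement, all of which follow confirmation. It therefore governs resumption. If sites can read it both ways, that is itself a reason to clarify it.

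A second reply is that relevant text may lie outside what can be seen. Section 8.5 refers sites to the Investigator's Brochure, and the list of tables names a table of known RAAS-blockade risks that does not appear in the public text. This limits the finding to the visible protocol. It gives no positive reason to think the gap is closed elsewhere.

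A third reply is that the risk is already well contained. The plan excludes potassium-sparing diuretics, drugs that may cause hyperkalemia, and eGFR below 45. It draws chemistry at every weekly dosing visit and bars dosing at 6.0 or above pending the retest. Appendix D grades this range as mild to moderate. All of this stands, and it is why the gap should matter uncommonly. It does not explain why a level that stops dosing once confirmed should allow dosing while confirmation is pending.

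Finally, delays have a price. The primary analysis uses the Per Protocol Set, which requires at least 7 of 9 doses, and about 30 subjects are planned. A spurious value could push a dose outside its window or lose the Day 3 dose. That cost is real but small: the set tolerates two missed doses, and the plan already accepts the same trade-off at 6.0 and above.

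**Conclusion.** The concern holds. On the visible text, an initial potassium of 5.5 to below 6.0 mmol/L without known new ECG changes can be followed by a dose while the retest is pending. The gap is open after six on-drug results and one pre-drug result per subject. In most schedules a prompt retest will come first; the margin disappears only with late retests or compressed visits.

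This rests on reading the last sentence of 8.5.4 as a resumption rule, on windows counted from nominal days, and on the Investigator's Brochure not adding its own bar, which could not be checked. The frequency of such values is unknown. The point concerns the safety of dosing and leaves sample size, alpha and the primary analysis method unchanged. It should be corrected; confidence is medium. Whether an ECG should be done at the first, unconfirmed value is a separate question that I do not address.

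**What to change.** Add one sentence to 8.5.4: after any initial potassium of 5.5 mmol/L or above during the Treatment Period, no further Study Drug is given until the retest result is available and is below 5.5 mmol/L.

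Allow a local-laboratory repeat where time is short, including before the Day 3 dose within its +2 day window. The local-draw advice in 6.2, repeated in Appendix A footnote 7, can be extended to potassium for this purpose. The SAP (3.7.3) summarizes only central values for potassium, so a local repeat would inform dosing and would not enter the summary tables.

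The cost is the added sentence and, if local repeats are allowed, a matching edit in 6.2 and footnote 7. The retest is already required and the visit schedule does not change. The downside is a short dose delay, or rarely a missed dose, when the first value proves spurious, for example from a hemolyzed sample.

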#### **8.5.5. Safety Monitoring for Blood Pressure**

Should a subject experience a BP measurement of  $\leq 90$  mmHg (systolic) a second measurement must be done within a 30-minute period. If the subject is symptomatic (i.e., dizziness, light-headedness, clammy skin, fatigue, blurry vision), at any point in the study, the subject should contact the Study Center immediately. If the confirmed SBP is  $\leq 90$  mmHg and/or the subject remains symptomatic, dosing of a subject with Study Drug will be paused. Oral and/or IV hydration should be instituted. The suitability of the subject for continued dosing will be determined by the Investigator in consultation with the Sponsor Medical Monitor after the SBP has normalized and/or subject is no longer symptomatic and will be based on the reversibility of initiating factors (e.g., decreased oral intake, cold/flu, other illness). If the subject remains symptomatic or if the SBP does not normalize Study Drug should be permanently discontinued (refer to Stopping Rules for BP Section 8.6.5).

### **8.6. Stopping Rules**

For the purposes of the renal and platelet stopping rules, Baseline is defined as:

- The last non-missing measurement prior to the first dose

#### **8.6.1. Stopping Rules for Liver Chemistry Elevations**

In the event of laboratory results meeting the following criteria, **and the event is without an alternative explanation as discussed with the Sponsor Medical Monitor**, dosing of a subject with Study Drug (ISIS 757456 or placebo) will be stopped permanently; values that are not confirmed due failure to retest or missing lab values will be presumed confirmed:

1. ALT or AST  $> 8$  x ULN, which is confirmed
2. ALT or AST  $> 5$  x ULN, which is confirmed and persists for  $\geq 2$  weeks
3. ALT or AST  $> 3$  x ULN, which is confirmed **and** total bilirubin  $> 2$  x ULN or INR  $> 1.5$

4. ALT or AST > 3 x ULN which is confirmed, **and** the new appearance (i.e., onset coincides with the changes in hepatic enzymes) of fatigue, nausea, vomiting, right upper quadrant pain or tenderness, fever, rash, and/or concomitant eosinophilia (> ULN)

### 8.6.2. Stopping Rules for Renal Function Test Results

In the event of laboratory results for either of the following criteria, dosing of a subject with Study Drug (ISIS 757456 or placebo) will be stopped permanently:

1. Confirmed serum creatinine increase that is both  $\geq 0.3$  mg/dL (26.5  $\mu$ mol/L) and  $\geq 40\%$  above Baseline creatinine values (refer to Section 8.6)
2. Confirmed 30% decline in eGFR from Baseline eGFR values
3. Confirmed proteinuria (UPCR  $\geq 0.5$  mg/mg)

The follow-up schedule for any events meeting either of these stopping criteria will be determined by the Investigator **in consultation with** the Sponsor Medical Monitor or designee. At the discretion of the Investigator, a decision to hold or permanently stop study drug may be made based on lesser changes in these parameters observed in isolation or in association with other renal-related abnormalities.

### 8.6.3. Stopping Rule for Platelet Count Results

In the event of any platelet count less than 75,000/mm^3, monitoring frequency and dosing should be adjusted as recommended in Table 6 below.

**Table 6: Actions in Subjects with Low Platelet Count**

Confirmed Platelet Count	Dosing	AESI?	Monitoring
$\geq 75,000/\text{mm}^3$	Yes	No	
 
● Monitor weekly
 

$< 75,000/\text{mm}^3$ to $50,000/\text{mm}^3$ , in the absence of MB or clinically relevant non-major bleeding (CRNMB) (defined below)	Pause	No	
 
● Monitor at least twice per week until 3 successive values above 75,000/mm^3. Then monitor weekly until values normalize.
 
● The suitability of the subject for continued dosing will be determined by the Investigator in consultation with the Sponsor Medical Monitor and will be based on factors such as the original rate of decline in the subject's platelet count, whether any bleeding events were experienced, and the speed of recovery of platelet count after interruption of dosing. The subject must have 3 successive values above 100,000/mm^3 before continued dosing is considered.
 
● Perform additional labs in Table 5
 

**Table 6: Actions in Subjects with Low Platelet Count (Continued)**

Confirmed Platelet Count	Dosing	AESI?	Monitoring
< 50,000/mm  to 25,000/mm 	Permanently Discontinue	Yes, if only accompanied by a MB event or CRNMB event, subject to 15-day expedited reporting	
 
• Monitor at least twice per week until 3 successive values above 75,000/mm^3. Then monitor weekly until values normalize
 
• A hematologist consultation may be considered at the discretion of the Investigator and Sponsor Medical Monitor
 
• Perform additional labs in Table 5
 

< 25,000/mm 	Permanently Discontinue	Yes, subject to 15-day expedited reporting	
 
• Monitor daily until 2 successive values above 25,000/mm^3. Then monitor twice per week until 3 successive values above 75,000/mm^3. Then monitor weekly until values normalize.
 
• Administration of steroids* and a hematologist consultation is recommended
 
• Perform additional labs in Table 5
 

< 10,000/mm 	Permanently Discontinue	Yes, subject to 15-day expedited reporting	
 
• Monitor daily until 2 successive values above 25,000/mm^3. Then monitor twice per week until 3 successive values above 75,000/mm^3. Then monitor weekly until values normalize.
 
• Hospitalize subject and expedite a hematologist consultation.
 
• Administer platelet transfusions and steroids*, if deemed necessary.
 
• Perform additional labs in Table 5
 

\* Treatment guidelines for immune thrombocytopenia ([Provan et al. 2010](#)) recommend Dexamethasone 40 mg daily for 4 days every 2–4 weeks for 1–4 cycles; Prednis(ol)one 0.5–2 mg/kg/d for 2–4 weeks then taper; or methylprednisolone 30 mg/kg/day for 7 days. (**Note:** Subject may require continuation with oral steroids after methylprednisolone).

### Definition of Major Bleeding Events ([Schulman and Kearon 2005](#))

1. Fatal bleeding, and/or
2. Symptomatic bleeding in a critical area or organ, such as intracranial, intraspinal, intraocular, retroperitoneal, intraarterial or pericardial, or intramuscular with compartment syndrome
3. Clinically overt bleeding leading to transfusion of  $\geq 2$  units of packed red blood cells or whole blood or a fall in hemoglobin of 2.0 mg/dL (1.24 mmol/L) or more within 24 hours

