### Definition of Clinically Relevant Non-Major Bleeding Events

Clinically-relevant non-major bleeding is defined as overt bleeding not meeting the criteria for MB but that resulted, for example, in medical examination, intervention, or had clinical consequences for a subject.

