### Definition of Minor Bleeding Events

Minor bleeding events are those that do not fulfill the criteria for MB or CRNMB (defined above), for example excess bruising, petechiae, gingival bleeding on brushing teeth.

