#### **9.3.4. AE of Special Interest (AESI)**

For the purpose of this study, severe reductions in platelet count  $< 50,000/\text{mm}^3$  accompanied by a MB event or CRNMB event, or platelet count of  $< 25,000/\text{mm}^3$  independent of a MB or CRNMB event are considered as AEs of special interest and should be subject to 15-day expedited reporting by the Sponsor to the regulatory agencies.

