**Appendix D Grading Scale for AEs Relating to Laboratory Abnormalities**

The following grading recommendations for AEs relating to lab test abnormalities and AEs at the injection site are based upon the CTCAE Version 5.0, November 2017.

Adverse Event	Mild	Moderate	Severe
Hematology			
aPTT prolonged	>ULN - 1.5 x ULN	>1.5 - 2.5 x ULN	>2.5 x ULN; bleeding
Eosinophils increased †	>ULN and >Baseline	-	Steroids Initiated
Fibrinogen decreased	<1.0 - 0.75 x LLN; if abnormal, <25% decrease from baseline	<0.75 - 0.5 x LLN; if abnormal, 25 - <50% decrease from baseline	<0.5 x LLN; if abnormal, ≥50% decrease from baseline
Hemoglobin decreased (Anemia)	Hemoglobin (Hgb) <LLN - 10.0 g/dL; <LLN - 6.2 mmol/L; <LLN - 100 g/L	Hgb <10.0 - 8.0 g/dL; <6.2 - 4.9 mmol/L; <100 - 80g/L	Hgb <8.0 g/dL; <4.9 mmol/L; <80 g/L; transfusion indicated
Hemoglobin increased**	Increase in >0 - 2 g/dL above ULN or above baseline if baseline is above ULN	Increase in >2 - 4 g/dL above ULN or above baseline if baseline is above ULN	Increase in >4 g/dL above ULN or above baseline if baseline is above ULN
INR increased	>1.2 - 1.5; >1 - 1.5 times above baseline if on anticoagulation	>1.5 - 2.5; >1.5 - 2.5 x baseline if on anticoagulation; monitoring only indicated	>2.5; >2.5 x baseline if on anticoagulation; dose adjustment indicated
Lymphocyte count decreased	<LLN - 800/mm  ; <LLN - 0.8 x 10  /L	<800 - 500/mm  ; <0.8 - 0.5 x 10  /L	<500 /mm  ; <0.5 x 10  /L
Lymphocyte count increased	-	>4000/mm  - 20,000/mm 	>20,000/mm 
Neutrophil count decreased	<LLN - 1500/mm  ; <LLN - 1.5 x 10  /L	<1500 - 1000/mm  ; <1.5 - 1.0 x 10  /L	<1000/mm  ; <1.0 x 10  /L
Platelet count decreased	<LLN - 75,000/mm  ; <LLN - 75.0 x 10  /L	<75,000 - 50,000/mm  ; <75.0 - 50.0 x 10  /L	<50,000/mm  ; <50.0 x 10  /L
White blood cell decreased	<LLN - 3000/mm  ; <LLN - 3.0 x 10  /L	<3000 - 2000/mm  ; <3.0 - 2.0 x 10  /L	<2000/mm  ; <2.0 x 10  /L
Chemistry			
Acidosis	pH <normal, but ≥7.3	-	pH <7.3

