### AE of special interest (AESI): Platelet reduction

Per protocol, severe reductions in platelet count  $< 50,000/\text{mm}^3$  accompanied by a major bleeding (MB) event or clinically-relevant non-major bleeding (CRNMB) event, or platelet count of  $< 25,000/\text{mm}^3$  independent of a MB or CRNMB event are considered as AESI. The AEs meeting the AESI criteria will be captured in the AE CRF page with a check box to indicate. AESI will be summarized by preferred term. A listing of AESI will also be provided.

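### The major-bleeding definition gives the haemoglobin fall as 2.0 mg/dL beside 1.24 mmol/L; by Appendix D's own conversion the first unit should be g/dL

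*Combined protocol and SAP*

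**What the plan says.** Protocol section 8.6.3 defines three classes of bleeding. Item 3 of the major bleeding (MB) definition covers clinically overt bleeding that leads either to transfusion of at least 2 units or to "a fall in hemoglobin of 2.0 mg/dL (1.24 mmol/L) or more within 24 hours". Clinically relevant non-major bleeding (CRNMB) is overt bleeding short of MB that resulted, for example, "in medical examination, intervention, or had clinical consequences for a subject". Minor bleeding is whatever meets neither definition, "for example excess bruising, petechiae, gingival bleeding on brushing teeth".

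These classes are used in four places:

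- **Table 6, 50,000 to below 75,000/mm³.** The row that pauses dosing applies "in the absence of MB or clinically relevant non-major bleeding (CRNMB) (defined below").
- **Table 6, 25,000 to below 50,000/mm³.** The AESI column reads "Yes, if only accompanied by a MB event or CRNMB event, subject to 15-day expedited reporting".
- **Protocol 9.3.4.** A count below 50,000/mm³ is an AESI when "accompanied by a MB event or CRNMB event, or platelet count of" less than 25,000/mm³ is an AESI regardless of bleeding.
- **SAP 3.7.2.** The AESI rule is repeated, followed by "The AEs meeting the AESI criteria will be captured in the AE CRF page with a check box to indicate". AESIs are then summarised and listed.

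Appendix D grades anaemia in three parallel units. Its moderate grade is "Hgb <10.0 - 8.0 g/dL; <6.2 - 4.9 mmol/L; <100 - 80g/L". It also grades haemoglobin increases in g/dL. Haemoglobin appears in mg/dL nowhere else in the documents, and nothing corrects or explains item 3.

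**The concern.** A threshold printed in two units should give the same answer in either. This one does not, and the gap is far too large to be rounding.

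The mg/dL figure comes first, and all the study centres are in the United States, so a site may work from it rather than from the bracketed value. That is an inference about practice; the protocol does not say so. A site that did would be applying a threshold below any fall a laboratory is likely to report. An otherwise minor overt bleed judged to have caused any measurable haemoglobin fall within 24 hours would then be recorded as major.

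With platelets from 25,000 to below 50,000/mm³, that label turns the event into an AESI, starts 15-day expedited reporting, and adds a case to the AESI summary and listing. From 50,000 to below 75,000/mm³, it takes the subject out of the Table 6 pause row.

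**Working it through.** **Inputs**

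- Item 3, section 8.6.3: 2.0 mg/dL and 1.24 mmol/L.
- Appendix D, anaemia boundaries: 10.0 g/dL = 6.2 mmol/L = 100 g/L, and 8.0 g/dL = 4.9 mmol/L = 80 g/L.

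**Step 1: conversion factor from Appendix D**

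- First pair: 6.2 / 10.0 = 0.62 mmol/L per g/dL (0.615 to 0.625 allowing for rounding of 6.2).
- Second pair: 4.9 / 8.0 = 0.6125 mmol/L per g/dL (0.606 to 0.619 allowing for rounding of 4.9).
- The two ranges overlap, so the pairs agree to rounding.

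**Step 2: try to reproduce the printed equivalence**

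- 2.0 mg/dL = 0.002 g/dL, and 0.002 × 0.62 = 0.00124 mmol/L. The protocol prints 1.24.
- Ratio: 1.24 / 0.00124 = 1000.
- The second pair gives 0.002 × 0.6125 = 0.001225 mmol/L. Neither pair reproduces the printed value.

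**Step 3: try g/dL instead**

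- 2.0 × 0.62 = 1.24 mmol/L, an exact match. The second pair gives 2.0 × 0.6125 = 1.225 mmol/L, a difference explained by the rounding of 4.9.
- In reverse: 1.24 / 0.62 = 2.0 g/dL = 2000 mg/dL.

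**Step 4: what the literal mg/dL figure would let in**

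The documents do not state the precision of haemoglobin reporting, so it is assumed here. The anaemia grades print haemoglobin to 0.1 g/dL.

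| Assumed reporting step | In mg/dL | Multiple of 2.0 mg/dL |
|---|---|---|
| 0.1 g/dL | 100 | 100 / 2.0 = 50 |
| 0.01 g/dL | 10 | 10 / 2.0 = 5 |

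At either precision, one reporting step already exceeds the printed figure. At 0.1 g/dL, the intended fall is 2.0 / 0.1 = 20 steps.

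As an illustration, take haemoglobin of 13.5 and then 13.4 g/dL within 24 hours. The fall is 0.1 × 0.62 = 0.062 mmol/L, and 0.062 / 1.24 = 5% of the intended threshold, yet it exceeds 2.0 mg/dL.

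**Step 5: which classifications can change**

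| Platelets (/mm³) | Effect if a minor bleed is relabelled MB |
|---|---|
| 50,000 to below 75,000 | Falls outside the pause row; no AESI rule applies |
| 25,000 to below 50,000 | Becomes an AESI with 15-day reporting; discontinuation applies anyway |
| Below 25,000 | None; AESI and discontinuation apply regardless of bleeding |

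Every fall of 2.0 g/dL or more also exceeds 2.0 mg/dL, so no true major bleed is missed. Every rule that uses these classes treats MB and CRNMB alike, so a bleed already classed as CRNMB is unaffected.

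**The case against.** The arithmetic is not in dispute. The case on the other side is that almost nothing follows from it.

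- **The bracket is right.** The correct threshold stands in the same phrase, so a careful reader can see what was meant. True, but the text still contradicts itself.
- **Item 3 is causal.** The bleeding must lead to the fall, so a chance change of 0.1 g/dL beside gingival bleeding does not qualify unless the investigator attributes it to the bleed. This stands: the example in Step 4 meets the number, not the whole item.
- **Gingival bleeding is a named example of minor bleeding.** This helps in practice. It does not settle the matter, because minor bleeding is defined as what fails the MB and CRNMB definitions.
- **Few subjects could be affected.** CRNMB is broad enough that a bleed worked up closely would often qualify already. Section 8.5.3 asks for coagulation tests and a platelet count after a minor bleed, not haemoglobin. Retests are ideally within 3 days and monitoring is at least twice weekly. Daily monitoring applies only below 25,000/mm³, where the error has no effect. All of this stands. Table 6 does call for the Table 5 tests, which include a blood count, below 75,000/mm³, although section 8.5.2 says only that they may be done. Haemoglobin is therefore likely to be measured again, but a pair within 24 hours is not routine.
- **The gap from 50,000 to below 75,000/mm³ exists anyway.** Table 6 has no row for that range with MB or CRNMB, whatever the unit. This also stands: the misprint could only send an extra case into it.

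These points limit the consequence. None of them makes the printed pair correct.

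**Conclusion.** The concern holds, as a minor correction. The mg/dL label is wrong by a factor of 1000 and the mmol/L figure is right. The conversion rests only on the protocol's own Appendix D. The statement that any reportable fall would pass the literal figure rests on an assumed reporting step of 0.1 or 0.01 g/dL.

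The main exposure is an otherwise minor bleed, with platelets from 25,000 to below 50,000/mm³, to which an investigator attributes a small haemoglobin fall within 24 hours. The direction of error is over-reporting only. Discontinuation below 50,000/mm³, sample size and the efficacy analyses are untouched. It is still worth correcting, because the definition decides whether an event goes to expedited reporting.

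**What to change.** In protocol section 8.6.3, Definition of Major Bleeding Events, item 3, replace mg/dL with g/dL so that the threshold is 2.0 g/dL (1.24 mmol/L). Tell sites to use the corrected definition when completing the AESI check box described in SAP 3.7.2.

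The cost is one unit label, issued by site memo or carried in the next amendment. Visits, sample size and analysis do not change.
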